5.3.2 Adjustments for Covariates of Interest

The primary, secondary, and exploratory efficacy endpoints will include the stratification variables (region, concurrent AD medication use, clinical disease staging), *ApoE4* status, and baseline value of the endpoint (if applicable) as covariates. For mixed-effects models for repeated measures (MMRM), the baseline-by-visit interaction will also be included. To follow ITT principle, the classification used at randomization will be used for the adjustments for covariates of interest.

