Time to worsening of CDR scores by 24 months

Time to worsening of CDR scores by 24 months will be analyzed on the FAS using a Cox regression model for treatment effect, adjusting for randomization stratification factors. Median, 1st quartile, and 3rd quartile of time to worsening of CDR scores and proportion of subjects with

worsening of CDR scores at 6, 12, 18, and 24 months will be estimated using Kaplan-Meier method based on time to worsening of CDR scores. Time to worsening of CDR scores is defined as time from randomization to worsening of the CDR scores (ie, the second worsening - increase from baseline by at least 0.5 points on the global CDR score, in 2 consecutive visits [at least 8 weeks apart]). For example, if the global CDR scores are 0.5 at baseline, 1.0 at Visit 6 [3 months visit], 1.0 at Visit 7 [6 months visit], this subject have worsening of CDR scores at Visit 7 [6 months visit]. If the global CDR scores are 0.5 at baseline, 1.0 at Visit 6 [3 months visit], 0.5 at Visit 7 [6 months visit], the subject does NOT have worsening of CDR scores at Visit 7 [6 months visit]). If randomization date is not same as the first dose date, the first dose date will be used instead of randomization date. If last available assessment shows worsening of the global CDR score, it will be considered as a censor. For subjects whose CDR scores have not worsened by the end of study, the time to worsening of CDR scores will be censored at the date of last CDR assessment for these subjects. All post-baseline assessments within Study Day 753 (upper limit of 24 months analysis visit for CDR assessment) will be included.

The same analysis by censoring the data after intercurrent events (treatment discontinuation, and initiation/change of AD medications) will be conducted as sensitivity analysis.

Time to conversion to dementia by 24 months for subjects who were not clinically staged as dementia at Baseline based on clinical diagnosis

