This endpoint will be analyzed on the FAS using a Cox regression model for treatment effect, adjusting for randomization stratification factors. Median, 1st quartile, 3rd quartile of time to conversion to dementia and proportion of subjects with dementia diagnosis at 6, 12, 18, and 24 months will be estimated using Kaplan-Meier method based on time to conversion to dementia in clinical diagnosis. Time to conversion to dementia for subjects who were not clinically staged as dementia at baseline is defined as time from randomization to conversion to dementia in clinical diagnosis. If randomization date is not same as the first dose date, the first dose date will be used instead of randomization date. For subjects without clinical dementia by the end of study, the time to conversion to dementia will be censored at the date of last dementia diagnosis for these subjects. All post-baseline assessments within Study Day 753 (upper limit of 24 months analysis visit for CDR assessment) will be included.

The same analysis by censoring the data after intercurrent events (treatment discontinuation, and initiation/change of AD medications) will be conducted as sensitivity analysis.

The diagnosis and clinical disease staging will be verified via a central review process and adjudicated if necessary (adjudication will only occur when there is a discrepancy between the diagnosis and clinical disease staging made by the site compared to that determined by the central review process; moreover, where adjudication is required, it will be undertaken by an independent assessor(s)).

The rate of change over time (mean slope) based on CDR-SB score over 24 months

The rate of change over time (mean slope) for the change from baseline in CDR-SB will be analyzed on the FAS using linear mixed effects (LME) models for multivariate normal data

derived from a random coefficient model (slope analysis), where the mean slope in each group depends on a continuous assessment time. The LME model will include assessment time, and treatment group-by-assessment time as well as random intercept and slope (unstructured). The Kenward-Roger approximation will be used to estimate the denominator degrees of freedom.

Other continuous endpoints

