The diagnosis and clinical disease staging will be verified via a central review process and adjudicated if necessary (adjudication will only occur when there is a discrepancy between the diagnosis and clinical disease staging made by the site compared to that determined by the central review process; moreover, where adjudication is required, it will be undertaken by an independent assessor(s)).

The rate of change over time (mean slope) based on CDR-SB score over 24 months

The rate of change over time (mean slope) for the change from baseline in CDR-SB will be analyzed using linear mixed effects (LME) models for multivariate normal data derived from a random coefficient model (slope analysis), where the mean slope in each group depends on a continuous assessment time. The LME model will include baseline CDR-SB, randomization stratification variables, assessment time, and treatment group-by-assessment time.

Other continuous endpoints

The other continuous secondary efficacy endpoints will be analyzed using the same MMRM model as the primary efficacy analysis to compare elenbecostat (E2609) 50 mg versus placebo on the FAS, using baseline value corresponding to the response variable in the model. These endpoints include:

- Change from baseline in CDR-SB at 27 months (ie, 24 months of treatment plus 3 months posttreatment follow-up)
- Change from baseline in ADAS-cog₁₄, MMSE, and FAQ at 24 months
- Change from baseline in ADAS-cog₁₄ Word List (immediate recall and delayed recall) at 24 months

With regard to the change from baseline in ADAS-cog₁₄ Word List, it includes the immediate and delayed recall tasks, their scores will be part of the ADAS-cog₁₄ assessment (Item 1 and 4).

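### The CDR-SB slope model lists none of the covariates that Section 5.3.2 requires, and the Cox models leave out ApoE4

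*SAP*

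**What the plan says.** SAP v2.0 Section 5.3.2 sets a general rule: "The primary, secondary, and exploratory efficacy endpoints will include the stratification variables (region, concurrent AD medication use, clinical disease staging"), followed by ApoE4 "status, and baseline value of the endpoint (if applicable) as covariates". It asks for one interaction, in one type of model: "For mixed-effects models for repeated measures (MMRM), the baseline-by-visit interaction will also be included".

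Section 5.4.2 then defines the individual secondary models:

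- **CDR-SB slope.** "The LME model will include assessment time, and treatment group-by-assessment time as well as random intercept and slope (unstructured"). No baseline score, stratification factor or ApoE4 term is named.
- **Time to worsening of CDR and time to conversion to dementia.** Both are analysed "using a Cox regression model for treatment effect, adjusting for randomization stratification factors". ApoE4 is not named in either.

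Section 5.4.4 analyses the NPI-10 slope in the same manner as the CDR-SB slope, and the time to change of concomitant AD treatment in the same manner as the time to dementia.

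**The concern.** The general rule and the model descriptions disagree within the current SAP. A programmer who follows 5.4.2 literally fits a slope model with no covariates and Cox models without ApoE4. A programmer who treats 5.3.2 as binding adds the missing terms. Both can claim to follow the plan, and their estimates will differ. For the Cox models the target also shifts, because a hazard ratio conditional on one more prognostic factor is not the same quantity as one without it.

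At stake is reproducibility of two named secondary analyses and one named slope analysis, together with two exploratory analyses that copy them. A covariate set left open is avoidable analyst discretion. Precision of the slope comparison is a possible further loss, and its size needs checking before it is claimed.

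**Working it through.** **Step 1: the texts side by side**

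| Analysis | Baseline | Strata | ApoE4 |
|---|---|---|---|
| Rule in 5.3.2 | if applicable | yes | yes |
| Primary MMRM, 5.4.1 | yes | yes | yes |
| ANCOVA after multiple imputation, 5.4.1 and Section 9 | yes | yes | yes |
| Tau PET and CSF ANCOVA, 5.4.3 | yes | yes | yes |
| CDR-SB slope, 5.4.2 | no | no | no |
| NPI-10 slope, 5.4.4 (by reference) | no | no | no |
| Two Cox models, 5.4.2 | – | yes | no |
| Time to change of AD treatment, 5.4.4 (by reference) | – | yes | no |

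Where the SAP wants the covariates it writes them out. Where it wants an exception it says so: the last-on-treatment versus follow-up MMRM in 5.4.2 explicitly drops the baseline-by-visit term. The slope and Cox descriptions do neither.

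**Step 2: the plan's own figure**

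The SAP gives no precision figure for the slope or Cox analyses. Its only relevant calculation is the sample size in Section 4, which supplies the mean and SD used below, and it reproduces.

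- Difference: 0.25 × 1.46 = 0.365; SD 2.05; two-sided alpha 0.05; power 90%.
- n per arm = 2 × (1.960 + 1.282)² × 2.05² / 0.365² ≈ 663 evaluable.
- With 30% dropout: 663 / 0.70, rounded up, = 948 per arm, or 1896 in total, against 1900 stated.

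**Step 3: does the omission cost precision in the slope?**

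Change from baseline was simulated at the eight post-baseline visits of Table 4 (days 85 to 729).

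- From the SAP: mean 24-month change 1.46 and SD 2.05.
- Assumed: residual SD 0.7, giving slope SD √(2.05² − 2 × 0.7²) = √3.2225 ≈ 1.80.
- Assumed: the share of slope variance explained by the covariates, half through baseline and half through an index standing for strata and ApoE4.
- Follow-up: either all eight visits, or truncated at random to between two and eight visits.

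Three random intercept-and-slope models were fitted: as written; with covariate main effects; and with main effects plus covariate-by-time. Each cell is the SE of treatment-by-time divided by its SE in the model as written. The first number is REML (300 subjects, mean of 3 datasets) and the second is maximum likelihood (1330 subjects, 1 dataset).

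| Share of slope variance | Follow-up | Main effects | Main effects + by-time |
|---|---|---|---|
| 5% | full | 1.000 / 1.005 | 0.975 / 0.994 |
| 5% | truncated | 0.989 / 0.998 | 0.980 / 0.993 |
| 10% | full | 1.002 / 1.007 | 0.956 / 0.981 |
| 10% | truncated | 0.990 / 1.001 | 0.968 / 0.987 |
| 20% | full | 1.004 / 1.009 | 0.918 / 0.949 |
| 20% | truncated | 0.990 / 1.002 | 0.942 / 0.969 |
| 30% | full | 1.005 / 1.011 | 0.880 / 0.913 |
| 30% | truncated | 0.988 / 1.002 | 0.914 / 0.947 |

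With a share of 0% (maximum likelihood only) the main-effects ratio was 0.996 with full and 0.985 with truncated follow-up.

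Main effects alone therefore give ratios from 0.985 to 1.011. They shift the level of a subject's change scores but do not explain why subjects differ in slope. With by-time terms the SE falls by 0.6% to 2.5% at a 5% share and by 3.1% to 8.2% at 20%.

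The Cox models were not quantified, because the SAP gives no event rates.

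**The case against.** The strongest reply is that 5.3.2 and 5.4.2 can be read together, with 5.4.2 as an abbreviated list that 5.3.2 completes. That reading is possible, but nothing in the text selects it, and the models that spell out every covariate point the other way. The qualifier on the baseline value gives some room on that one term; it does not cover the strata or ApoE4.

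It is also fair to say that omitting covariates does not bias a randomised comparison, and that these endpoints are not confirmatory: Section 5.3.3 leaves other secondary and exploratory endpoints outside the hierarchy. Both points stand and limit the importance of the finding.

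Four stronger readings are tempting, and the document does not support them:

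- **Departing from 5.3.2 in itself loses precision.** For this model 5.3.2 asks only for main effects, and those change almost nothing. A gain needs by-time terms that 5.3.2 does not require here. Regressing per-subject slopes on covariates with assumed shares of 5%, 10% and 15% gives an unadjusted SE 2.4%, 5.0% and 8.2% larger, but this is close to 1/√(1 − share) = 1.026, 1.054 and 1.085, so it largely restates the assumption.
- **Covariates were removed without being recorded.** SAP v1.0 did have them: "The LME model will include baseline CDR-SB, randomization stratification variables, assessment time, and treatment group-by-assessment time". But v1.0 is superseded, and Section 7 of v2.0 is not a complete log of differences from it. For example, it also omits the per-protocol compliance limit moving from 80% to 67% and ApoE4 entering the primary model.
- **The slope is the analysis that best uses partial follow-up after early termination.** The SAP does not say so, and the primary MMRM also uses all observed post-baseline data.
- **Chance imbalance is left uncorrected.** Randomisation was stratified by region, staging and AD medication, which limits imbalance on those three factors.

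**Conclusion.** The contradiction holds on the current text alone. The CDR-SB slope model and, by reference, the NPI-10 slope omit every covariate that 5.3.2 names; the two secondary Cox models and, by reference, the time to change of AD treatment omit ApoE4. It is worth correcting because it leaves the fitted model open.

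The cost in precision is modest and conditional. Restoring the 5.3.2 main effects leaves the slope SE within about 1.5%. Covariate-by-time terms would reduce it by roughly 1% to 3% if the covariates explain 5% of slope variance and by 3% to 8% at 20%. This rests on the assumed shares, a residual SD of 0.7 and a small number of simulated datasets. Primary inference and familywise error are unaffected.

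**What to change.** 1. In the 5.4.2 slope model, list baseline CDR-SB, region, staging, AD medication use and ApoE4 alongside time and treatment-by-time, keeping the random intercept and slope. In 5.4.4, specify the same for the NPI-10 slope with baseline NPI-10.
2. Add covariate-by-time terms, for example baseline-, staging- and ApoE4-by-time, since these are what adjust a slope. Add a matching sentence to 5.3.2, next to the baseline-by-visit rule for the MMRM, so that no new mismatch arises. State that each group's mean slope is evaluated at the covariate means.
3. Add ApoE4 to both Cox models in 5.4.2; the time to change of AD treatment then follows by reference.

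If the simpler models were intended, naming them as exceptions in 5.3.2 also removes the contradiction, but forgoes the possible gain in precision.

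The cost is SAP wording and model statements. If ApoE4 is coded in two levels, the slope model gains 6 (region) + 1 + 1 + 1 + 1 = 10 main-effect parameters and 3 by-time parameters. No new data are needed.

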3.1.2 Secondary Objectives

The key secondary objectives of the Core Study are as follows:

- To determine whether elenbecestat is superior to placebo on the change from baseline in Alzheimer's Disease Composite Score (ADCOMS) at 24 months in subjects with EAD pooled across studies E2609-G000-301 and E2609-G000-302
- To determine whether elenbecestat is superior to placebo on brain amyloid levels at 24 months as measured by amyloid positron emission tomography (PET) in subjects with EAD pooled across studies E2609-G000-301 and E2609-G000-302
- To determine whether elenbecestat is superior to placebo on brain amyloid levels at 24 months as measured by amyloid PET in subjects with EAD in study E2609-G000-301
- To determine whether elenbecestat is superior to placebo on brain amyloid levels at 24 months as measured by amyloid PET in subjects with EAD in study E2609-G000-302

The other secondary objectives of the Core Study are as follows:

- To evaluate the safety and tolerability of elenbecestat in subjects with EAD
- To determine whether elenbecestat is superior to placebo on the change from baseline in the CDR-SB at 24 months for subjects with EAD enriched by baseline PET standardized uptake value ratio (SUVR) pooled across studies E2609-G000-301 and E2609-G000-302

- To determine whether elenbecestat is superior to placebo on the change from baseline in the ADCOMS at 24 months for subjects with EAD enriched by baseline PET SUVR pooled across studies E2609-G000-301 and E2609-G000-302
- To determine whether elenbecestat is superior to placebo on the rate of change over time (mean slope) based on CDR-SB score over 24 months in subjects with EAD pooled across studies E2609-G000-301 and E2609-G000-302
- To determine whether elenbecestat is superior to placebo on the time to worsening of Clinical Dementia Rating (CDR) scores in subjects with EAD pooled across studies E2609-G000-301 and E2609-G000-302
- To determine whether elenbecestat is superior to placebo on the time to conversion to dementia for subjects who were not clinically staged as having dementia at Baseline based on a clinical diagnosis evaluated every 3 months in the subjects with EAD pooled across studies E2609-G000-301 and E2609-G000-302
- To determine whether elenbecestat is superior to placebo on the change from baseline in CDR-SB at 27 months (ie, 24 months of treatment plus 3 months posttreatment follow up) in subjects with EAD pooled across studies E2609-G000-301 and E2609-G000-302

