- To determine whether elenbecestat is superior to placebo on the Alzheimer's Disease Assessment Scale-Cognition₁₄ (ADAS-cog₁₄), Mini Mental State Examination (MMSE), and Functional Assessment Questionnaire (FAQ) at 24 months in subjects with EAD pooled across studies E2609-G000-301 and E2609-G000-302
- To determine whether elenbecestat is superior to placebo on the ADAS-cog₁₄ Word List (immediate recall and delayed recall) at 24 months in subjects with EAD pooled across studies E2609-G000-301 and E2609-G000-302
- To evaluate the relationship between clinical changes at 24 months (CDR-SB, ADCOMS, ADAS-cog₁₄, MMSE, and FAQ) and changes in biomarkers that reflect disease progression (eg, cerebrospinal fluid [CSF] amyloid beta [A β] total tau [t-tau] and phosphorylated-tau [ptau], amyloid PET, tau PET, volumetric magnetic resonance imaging [vMRI] , functional magnetic resonance imaging [fMRI]) at 24 months in subjects with EAD pooled across studies E2609-G000-301 and E2609-G000-302
- To evaluate the population pharmacokinetics (PK) of elenbecestat in subjects with EAD

Based on the DSMB analyses, the evaluation of ADAS-cog₁₁ will be added as one of other secondary objectives of the Core Study.

The following secondary objective will be added to evaluate change from last dose in clinical assessments instead of the analysis for the change from baseline in CDR-SB at 27 months described above.

- To evaluate the change after last dose in CDR-SB, ADCOMS, ADAS-cog₁₁, ADAS-cog₁₄, MMSE, ADAS-cog₁₄ Word List (immediate recall and delayed recall) in subjects with EAD pooled across studies E2609-G000-301 and E2609-G000-302

As the study E2609-G000-301 and study E2609-G000-302 were terminated early there is a smaller sample size than originally planned, therefore the following key secondary objective will be removed:

- To determine whether elenbecestat is superior to placebo on brain amyloid levels at 24 months as measured by amyloid PET in subjects with EAD in each study (E2609-G000-301 and E2609-G000-302)

As the study E2609-G000-301 and study E2609-G000-302 were terminated early, the following objective will not be conducted:

- To evaluate the population pharmacokinetics (PK) of elenbecestat in subjects with EAD

The analyses for the following objectives will be reported separately from the CSR because of the timing of data availability.

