5.1.2 SECONDARY ENDPOINTS

The key secondary endpoints of the study are as follows

- Change from baseline in ADCOMS at 24 months in the combined studies
- Change from baseline in amyloid PET SUVR at 24 months for brain amyloid levels in the combined studies
- Change from baseline in amyloid PET SUVR at 24 months for brain amyloid levels in the individual studies

The other secondary endpoints of the study are as follows

- Change from baseline in the CDR-SB at 24 months for subjects enriched by baseline PET SUVR, eg, between 1.2 and 1.6, in the combined studies
- Change from baseline in the ADCOMS at 24 months for subjects enriched by baseline PET SUVR, eg, between 1.2 and 1.6, in the combined studies
- The rate of change over time (mean slope) based on CDR-SB score over 24 months in the combined studies

- Time to worsening of CDR scores by 24 months (eg, the worsening of global CDR score is defined as an increase from baseline by at least 0.5 points on the global CDR scale on 2 consecutive scheduled visits at which global CDR is undertaken) in the combined studies
- Time to conversion to dementia by 24 months for subjects who were not clinically staged as dementia at Baseline based on clinical diagnosis in the combined studies
- Change from baseline in CDR-SB at 27 months (ie, 24 months of treatment plus 3 months posttreatment follow-up) in the combined studies
- Change from baseline in ADAS-cog₁₄, MMSE, and FAQ at 24 months in the combined studies
- Change from baseline in ADAS-cog₁₄ Word List (immediate recall and delayed recall) at 24 months in the combined studies

Based on the DSMB analyses, the change from baseline in ADAS-cog₁₁ will be added as one of other secondary endpoints.

The following secondary endpoint will be added to evaluate the change after last dose instead of the change from baseline in CDR-SB at 27 months described above.

- Change from last dose to follow-up in CDR-SB, ADCOMS, ADAS-cog₁₁, ADAS-cog₁₄, MMSE, ADAS-cog₁₄ Word List (immediate recall and delayed recall) in the combined studies

As the study E2609-G000-301 and study E2609-G000-302 were terminated early, the sample size for amyloid PET SUVR is smaller than originally planned. Therefore the following key secondary endpoint will be removed.

- Change from baseline in amyloid PET SUVR at 24 months for brain amyloid levels in the individual studies

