5.4 EFFICACY ANALYSES

5.4.1 Primary Efficacy Analysis

Regarding the primary endpoint, the null hypothesis is that there is no difference in the mean change from baseline in CDR-SB at 24 months between elenbecestat 50 mg per day and placebo; the corresponding alternative hypothesis is that there is a difference in the mean change from baseline in CDR-SB at 24 months between elenbecestat 50 mg per day and placebo.

The primary analysis will be based on the ITT philosophy without regard to adherence to treatment. All observed data will be included in the primary analysis, regardless of treatment discontinuation or change in concomitant AD medications. The primary analysis of the change from baseline in CDR-SB at 24 months will be performed to compare elenbecestat 50 mg per day versus placebo using a MMRM on the FAS. The MMRM model will include baseline CDR-SB and baseline CDR-SB by visit interaction as a covariate, with treatment group, visit, randomization stratification variables (ie, region [7 levels], clinical disease staging [MCI due to AD, early stage of mild AD], and concurrent AD medication use at randomization (Visit 2) [yes, no]), *ApoE4* status, and treatment group-by-visit interaction as fixed effects. An unstructured covariance matrix will be employed to model the covariance of within subject effect and the Kenward-Roger approximation will be used to estimate the denominator degrees of freedom; if MMRM fails to converge then a covariance structure with fewer parameters from the following list will be employed according to the prespecified order in the list until the MMRM converges. The list of covariance structure will include Heterogeneous Toeplitz, Toeplitz, Heterogeneous Compound Symmetry, and Compound Symmetry. If a structured covariance is used, then the sandwich estimator will be used to estimate variance of the treatment effect estimator.

This primary analysis will include all observed post baseline data of the change from baseline in CDR-SB without imputation of missing values. The least squares (LS) means and difference in

LS means between elenbecostat treatment group and placebo, and corresponding 95% confidence interval (CI) will be presented.

Sensitivity/Supplementary Analyses

- 1). An MMRM analysis will be performed on the PPS.

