The other continuous secondary efficacy endpoints will be analyzed using the same MMRM model as the primary efficacy analysis to compare elenbecestat 50 mg versus placebo on the FAS, using baseline value corresponding to the response variable in the model. These endpoints include:

- Change from baseline in the CDR-SB at 24 months for subjects enriched by baseline PET SUVR, eg, between 1.2 and 1.6, in the combined studies
- Change from baseline in the ADCOMS at 24 months for subjects enriched by baseline PET SUVR, eg, between 1.2 and 1.6, in the combined studies
- Change from baseline in ADAS-cog₁₁, ADAS-cog₁₄, MMSE, and FAQ at 24 months in the combined studies
- Change from baseline in ADAS-cog₁₄ Word List (immediate recall and delayed recall) at 24 months in the combined studies

The following amyloid PET mean composite SUVR in centiloid scale ([Adamczuk, 2019](#)) will be used to enrich the population, extrapolated from the 1.2 to 1.6 SUVR calculated for Florbetapir ([Dhadda, 2018](#)) : 37.234 to 119.522 (equivalent to 1.198633 to 1.667324 in Florbetaben and 1.212557 to 1.777799 in Flutemetamol) (Adamczuk [2019])

With regard to the change from baseline in ADAS-cog₁₄ Word List, it includes the immediate and delayed recall tasks, their scores will be part of the ADAS-cog₁₄ assessment (Item 1 and 4).

For ADAS-cog₁₁, ADAS-cog₁₄, MMSE, FAQ, and ADAS-cog₁₄ Word List (immediate recall and delayed recall), the MMRM analysis will be conducted on FAS, by censoring the data after intercurrent events (treatment discontinuation, and initiation/change of AD medications) as sensitivity analyses.

The MMRM using the change from baseline at last on treatment visit and 12 week Follow-up visit will be conducted based on the subjects in FAS who have the assessments at both visits to evaluate the change after last dose in CDR-SB, ADCOMS, ADAS-cog₁₁, ADAS-cog₁₄, MMSE, and ADAS-cog₁₄ Word List (immediate recall and delayed recall) instead of the analysis for the change from baseline in CDR-SB at 27 months. The same MMRM as the primary efficacy analysis (except excluding baseline by visit interaction) will be used with appropriate contrast to evaluate the difference between last on treatment visit and 12 week Follow-up visit by each treatment group.

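### The change-after-last-dose analysis prespecifies only within-arm contrasts; the between-arm contrast that would remove natural progression is not named

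*SAP*

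**What the plan says.** Section 3.1.2 first lists a 27-month objective framed against placebo: "To determine whether elenbecestat is superior to placebo on the change from baseline in CDR-SB at 27 months". It then adds a post-dose objective, "To evaluate the change after last dose in CDR-SB, ADCOMS" and further measures, to be evaluated "instead of the analysis for the change from baseline in CDR-SB at 27 months described above". The matching endpoint in Section 5.1.2 is "Change from last dose to follow-up in CDR-SB, ADCOMS" and so on. Neither the added objective nor the added endpoint names a comparator, and Section 7 records the substitution without one.

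The analysis is in Section 5.4.2, under the other continuous endpoints. It "will be conducted based on the subjects in FAS who have the assessments at both visits". The only contrast that the section names for it is "with appropriate contrast to evaluate the difference between last on treatment visit and 12 week Follow-up visit by each treatment group". As to the model, the section says: "The same MMRM as the primary efficacy analysis (except excluding baseline by visit interaction) will be used". The primary model in Section 5.4.1 contains treatment group, visit "and treatment group-by-visit interaction as fixed effects", so the interaction carries over.

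Section 5.4.2 does say that the other continuous endpoints are analysed to compare elenbecestat with placebo. That sentence introduces a list of 24-month endpoints, and change after last dose is not on it.

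**The concern.** Subjects with early Alzheimer's disease are expected to worsen over the post-dose interval whether or not they were on drug. A contrast of two visits within one arm therefore has a non-zero expected value even when stopping drug does nothing. It also absorbs practice effects.

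Two misreadings follow. A significant worsening after the last dose on elenbecestat could be taken as harm from withdrawal when it is ordinary progression. Conversely, an improvement after stopping drug could be offset by progression and go unseen. Setting the two within-arm results side by side does not solve this, because one can be significant and the other not when the underlying changes are identical.

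The same contrast is planned for CDR-SB, ADCOMS, ADAS-cog11, ADAS-cog14, MMSE and the ADAS-cog14 Word List.

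**Working it through.** **Inputs from the SAP**
- Placebo change in CDR-SB at 24 months: mean 1.46, SD 2.05 (Section 4).
- Target day of the 24-month visit: 729 (Section 8.2, Table 4).
- 12-week follow-up: the assessment closest to last dose + 84 days, in a window opening at 57 days. Last on treatment: the last post-baseline assessment on or before last dose (Section 8.2).
- All tests at the two-sided 5% level (Section 5).

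**Inputs not in the SAP, assumed**
- SD of the change between the two visits: 0.8, 1.2, 1.6.
- Subjects per arm with both visits: 200 or 400.
- Linear progression at the planned placebo rate.

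**Check on the planning inputs.** The SAP gives no figure for this analysis, but its sample size reproduces. Difference = 0.25 × 1.46 = 0.365. n per arm = 2 × (1.96 + 1.2816)² × 2.05² / 0.365² = 663. Allowing 30% dropout, 663 / 0.70 = 948 per arm, 1896 in total, against 1900 stated. The sample size is not in dispute.

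**Expected drift with no drug effect** = (1.46 / 729) × days between visits
- 84 days: 0.168 points.
- 129 days (last on-treatment visit 45 days before last dose): 0.258.
- 175 days (91 days before): 0.350.
- 57 days (earliest follow-up, last on-treatment visit on the day of last dose): 0.114.

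**Chance that a within-arm test is significant with no withdrawal effect, 84 days**
SE = SD / √n; probability = Φ(0.168 / SE − 1.96), the opposite tail being negligible.

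| SD of change | 200 per arm: SE | Probability | 400 per arm: SE | Probability |
|---|---|---|---|---|
| 0.8 | 0.057 | 0.85 | 0.040 | 0.99 |
| 1.2 | 0.085 | 0.51 | 0.060 | 0.80 |
| 1.6 | 0.113 | 0.32 | 0.080 | 0.56 |

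The lowest entry is more than six times the nominal 5%.

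**Comparing the two within-arm results by eye.** With equal drift and probability p of significance in each arm, exactly one arm is significant with probability 2p(1 − p). At SD 1.2 this is 2 × 0.80 × 0.20 = 0.32 with 400 per arm, and 2 × 0.51 × 0.49 = 0.50 with 200 per arm.

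**Masking.** Higher CDR-SB is worse, so drift is positive and reversal is negative. If stopping drug improved the score by 0.168 over the 84 days, the expected within-arm change on elenbecestat would be 0.168 − 0.168 = 0.

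**Between-arm contrast.** (Follow-up − last on treatment) on elenbecestat minus the same on placebo: drift common to both arms cancels, so the expected value is 0 and the type I error 5% when withdrawal has no effect. SE = SD × √(2 / n). For SD 1.2 and 400 per arm this is 0.085, against 0.060 within one arm, giving a 95% half-width of 1.96 × 0.085 = 0.17. Across the table, the SE runs from 0.057 (SD 0.8, 400 per arm) to 0.160 (SD 1.6, 200 per arm).

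**The case against.** A reader might infer that withdrawal and progression cannot be separated at all. The documents do not support that. The placebo arm is in the model, its own post-dose change is reported, and the treatment-by-visit term is fitted. From the two within-arm estimates and standard errors, a reader could form the difference in change and, treating the arms as approximately independent, its standard error. What is missing is the prespecified contrast, not the control information.

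A reader might also infer that drift would be mistaken for reversal of cognitive decline. It would not: progression raises CDR-SB and reversal lowers it, so drift masks reversal. The probabilities above concern apparent worsening. A clear within-arm improvement against expected progression would carry some information, although practice effects would still call for the placebo comparison.

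The added objective is to evaluate change, not to show superiority or reversibility, and a within-arm contrast fits that wording. The DSMB form of 11 September 2019 reports detrimental cognitive trends on drug, but nothing ties this analysis to it; Section 7 lists the additions prompted by DSMB analyses separately. Reversibility is a natural question here, but not a stated purpose.

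The numbers with both visits and the SD of change are unknown, and the interval varies between subjects, so the probabilities illustrate and do not predict. The endpoint is also an other secondary one without multiplicity control (Section 5.3.3).

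All of this limits the size and reach of the point. It does not supply the missing contrast: whatever the descriptive purpose, the within-arm change has no clear reading without the placebo change subtracted.

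**Conclusion.** The point holds in a limited form. For change after last dose, the SAP prespecifies a within-arm contrast only, in place of a placebo-controlled comparison at 27 months. At the planned placebo rate, progression contributes about 0.17 CDR-SB points over 84 days, more if the last on-treatment visit precedes the last dose and less if follow-up falls early in its window. With no withdrawal effect and an 84-day interval, the chance of a significant within-arm result is about 0.32 to 0.99 over the assumed range. This rests on linear progression and on assumed SDs and numbers with both visits. It is worked for CDR-SB only, since the SAP gives no rate for the other measures.

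Two further inferences should be avoided. The between-arm contrast would not fully restore a randomised comparison, because having both assessments is determined after randomisation and the interval between visits still varies. Nor does the point touch the primary or key secondary conclusions; it concerns how the post-dose results are read.

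**What to change.** In Section 5.4.2, state that the main contrast for each listed measure is the change from last on treatment to 12-week follow-up on elenbecestat minus the same change on placebo, taken from the treatment-by-visit term of the specified MMRM, with a 95% CI. Keep the within-arm changes as descriptive. Word the added objective and endpoint in Sections 3.1.2 and 5.1.2 to match.

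Add a sentence saying that the contrast is limited to FAS subjects with both assessments and is therefore not a full randomised comparison.

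Cost: one ESTIMATE or LSMESTIMATE statement per model and a few lines of SAP text. No new data and no change of model. The between-arm standard error is √2 times the within-arm one for equal arms, so the interval is wider.
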